1.3 STUDY CALENDAR

Assessments	Screening 28-day window up to Day 1 of treatment ¹	Day 1 of Every ODD Cycles (1, 3, 5...) +/- 5 days	Day 1 of every EVEN cycle Cycles (2, 4, 6...) +/- 5 days	END of Treatment Visit ²	Follow Up ³ (every 3M from EOT Visit
Informed Consent ⁴	X				
Inclusion/Exclusion Criteria	X				
Medical History/ Prior Treatment ⁵	X				
Concomitant medications	X	X	X	X	
Physical Exam	X	X	X	X	
Performance Status (ECOG or KPS)	X	X	X	X	
Vital signs/Weight/Height ⁶	X	X	X	X	
Drug Toxicity Assessment ⁷	X	X	X	X	
Baseline daily stool count	X				
ECG ⁸	X ⁹	EVERY 12 weeks (Pre- Cycle 5, 9, 13, ...)		X	
ECHO- 2D/MUGA	X				
Pregnancy test ¹⁰	X				
CBC with Differential ¹¹	X	X	X	X	
Chemistries ¹²	X	X	X	X	
PT/INR and PTT ¹³	X			X	
Urinalysis and UPC	X	X	X	X	
Thyroid Function Tests ¹⁴	X		X	X	
Amylase, Lipase	X	Every 12 weeks (Pre-Cycle 5, 9, 13...)		X	
Hepatitis B and C ¹⁵	X				
Tumor Imaging- CT Chest/Abdomen/Pelvis ¹⁶	X	Every 12 weeks (Pre- Cycle 5, 9, 13...)		X	
Brain MRI ¹⁷	X				
Pill Diary/Pill Count ¹⁸		X	X	X	
Research Blood ¹⁹ Phase II only	X	At week 7 (+/- 1 week) and progression			
Archival Tissue ²⁰ Phase II only	X				
Tissue Biopsy ²¹ Phase II Part 2 only	X	At week 7 (+/- 1 week) and progression			
Cabozantinib PO		Daily	Daily		
Pembrolizumab IV (30- minute infusion)		Day 1 of each Cycle			
Survival Status					X

¹ Routine laboratory tests for screening should be performed within 14 days of cycle 1.

² End of treatment visit will be completed 30 days (+/- 7 days) from date of last dose of study drug or before another treatment starts whichever occurs first.

³ Subjects will be followed for survival and progression post treatment every 3 months x 2 years, every 6 months x 3 years and yearly until death. Every 3 months from EOT visit.

⁴ Written consent must be obtained prior to performing any protocol specific procedure. Results of a test performed as part of routine clinical management are acceptable in –lieu of a screening test if performed within the specified time frame. (e.g., within 28 days period to Cycle 1 Day 1.)

⁵ Report complete medication history for 30 days prior to the screening visit. Medical history should include history of treatment for the primary diagnosis, including prior systemic, radiation treatment and surgical treatment and best response to prior systemic treatments. Date of last prior cancer treatment must be documented.

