with treatment naïve advanced melanoma. To evaluate the disease control rate (DCR) with the combination of cabozantinib and pembrolizumab in subjects with treatment naïve advanced melanoma. To evaluate the progression-free survival from the combination of cabozantinib and pembrolizumab in subjects with treatment naïve advanced melanoma. To evaluate the overall survival with the combination cabozantinib and pembrolizumab in subjects with treatment naïve advanced melanoma.	response (PR) per RECIST v1.1 criteria. Time to response per RECIST v1.1 criteria. DCR defined as the percentage of patients achieving CR + PR + SD at any time during the study following initiation of therapy. Radiologic progression-free survival (PFS) per RECIST v1.1 criteria. PFS is defined as the time between the first dose of study therapy and the earliest date of progression or death. Subjects who have neither progressed nor died will be censored at the last tumor assessment date for PFS. Overall survival defined as the time between the first dose of study therapy and death (subjects who have not died will be censored at the most recent last-known-alive date).	
Tertiary/Exploratory		
Biomarker evaluation: To assess changes in tumor biomarkers.	Blood samples and biopsy samples will be collected to evaluate for biomarkers and changes in tumor microenvironment.	

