6.1.2 DOSING AND ADMINISTRATION

6.1.2.1 DOSING:

Cabozantinib will be administered in a tablet form. The drug is taken continuously for 21 days or 3 weeks. This period of time is defined as one treatment cycle. Side effects are monitored, and dose modifications permitted as per a prescribed algorithm. Cabozantinib to continue per PI discretion.

A fixed dose of 200 mg of pembrolizumab will be administered via intravenous infusion Q3W for up to 2 years.

6.1.2.2 ADMINISTRATION:

Pembrolizumab 200 mg will be administered as a 30-minute infusion Q3W. Sites should make every effort to target infusion timing to be as close to 30 minutes as possible. However, given the variability of infusion pumps from site to site, a window of -5 minutes and +10 minutes is permitted (i.e., infusion time is 30 minutes: -5 min/+10 min).

6.1.2.3 DOSE MODIFICATION AND INTERRUPTION:

Subjects will be monitored for AEs from the time of signing informed consent through 30 days after the last dose of cabozantinib and/or pembrolizumab treatment. Subjects will be instructed to notify their physician immediately for any occurring AE. Causality assessment of AEs should include at minimum confounding factors such as disease and concomitant medications. Adverse event severity will be graded by the investigator according to CTCAE v. 4.0.

The following should be taken into consideration in decisions regarding dose modifications (reductions or interruption):

- As a general approach, all AEs should be managed with supportive care at the earliest signs of toxicity considered related to study treatment. Should this be ineffective, dose reductions or interruptions should be considered to prevent worsening of toxicity.
- If the etiology of AEs is unclear the first dose reduction must be made to cabozantinib then pembrolizumab depending on toxicity profile
- Dose modification criteria for cabozantinib for phase 2 part of the trial will be finalized based on the final dosing selected from the phase 1 trial. Dose reductions and/or interruptions should be implemented for unacceptable toxicity. Doses may be modified at any time while on study.
- Dose reductions or interruptions may also occur in the setting of lower grade toxicity than defined in Table below, if the investigator feels it is in the interest of a subject's safety and will optimize drug tolerability.

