should be sent to the subject (or the subject's legal guardian) requesting contact with the clinic. If a subject is discontinued from study treatment because of an AE considered to be related to study treatment and the event is ongoing 30 days after the last dose of study treatment, the event must be followed until resolution or determination by the investigator that the event has become stable or irreversible.

If a subject withdraws consent to participate in the study, the reason for withdrawal will be documented, no further study procedures or assessments will be performed, and no further study data will be collected for this subject, other than the determination of survival status from public records such as government vital statistics or obituaries.

Patients that withdraw from study treatment (but not their consent for follow-up) for reasons other than progression will continue to have scans per study calendar until PD is noted.

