8.3.4.2 End of treatment and premature withdrawal visit

Required observations following the completion of protocol therapy: Follow-up visits may be performed +/- 7 days from the targeted study visit date. Laboratory evaluations may be collected up to 24 hours prior to study visit without being a deviation.

Patients will be followed for survival and progression every 3 months for 2 years, every 6 months for 3 years and yearly until death. Follow-up will be performed using telephone contact, correspondence with treating physicians, and death records as necessary to update vital status.

Adverse events	Capture all AEs observed for 30 days after last dose of treatment. After 30 days, only SAEs that are at least possibly attributed to the study drug are required to be captured
Concomitant medications	Capture all concomitant medications for 30 days after last dose of treatment or until a new treatment is started, whichever occurs first.

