9.4.3 ANALYSIS OF THE SECONDARY ENDPOINT(S)

The secondary efficacy endpoints (DCR, PFS and OS) will be summarized descriptively using the mITT population.

DCR

DCR is defined as the proportion of patients with RECIST disease control (CR, PR, or SD). All patients that do not meet the criteria for an objective response by the analysis cutoff date will be considered non-responders. A binomial proportion with 95% exact confidence interval will be reported.

PFS

PFS will be defined as the time from treatment initiation to the date of first documentation of disease progression or death due to any cause in the absence of documented progression. For patients who discontinue study treatment due to reasons other than progression or death, the patient will be censored at their last radiographic assessment for progression. Cumulative PFS will be descriptively summarized over time with the method of Kaplan-Meier.

OS

OS will be defined as the time from treatment initiation to the date of death due to any cause. Cumulative OS will be descriptively summarized over time with the method of Kaplan-Meier.

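### Section 9.4.3 censors PFS when treatment stops without progression, against Sections 3 and 8.1 and the planned follow-up to progression; the direction of bias depends on the censoring scan and on risk after stopping

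*Combined protocol and SAP*

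**What the plan says.** Section 9.4.3 defines PFS as running from treatment initiation to "the date of first documentation of disease progression or death due to any cause in the absence of documented progression". Nothing there limits events to the treatment period. The next sentence is the censoring rule: "For patients who discontinue study treatment due to reasons other than progression or death, the patient will be censored at their last radiographic assessment". Its only trigger is stopping treatment; it does not require the patient to stay event-free afterwards.

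Section 3 has a different rule, which Section 8.1 repeats: "Subjects who have neither progressed nor died will be censored at the last tumor assessment date for PFS". Treatment status plays no part in it.

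Three places plan follow-up for progression after treatment:

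- Section 7.2: patients who stop treatment but keep their consent for follow-up, "for reasons other than progression will continue to have scans per study calendar until PD is noted".
- Section 1.3, footnote 3: "Subjects will be followed for survival and progression post treatment every 3 months x 2 years".
- Section 8.3.4.2: "Patients will be followed for survival and progression every 3 months for 2 years".

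Two smaller wording points are nearby. The DCR paragraph of 9.4.3 first defines disease control correctly as CR, PR or SD, then carries over a sentence from the ORR paragraph: "All patients that do not meet the criteria for an objective response by the analysis cutoff date will be considered non-responders". Section 8.1 gives the name duration of response to a time that starts at CR, PR or SD. The synopsis and Section 4.1 call that endpoint the duration of DCR, and Appendix A starts duration of response at CR or PR.

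**The concern.** Take a patient who stops for toxicity at month 3 and has documented progression at month 8. Under Sections 3 and 8.1 this is an event at month 8. Under the literal 9.4.3 rule the patient is censored and the progression is not counted. The statistician programs from 9.4.3, so the choice of section decides the curve.

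The censoring date is also open. The last radiographic assessment could be the last on-treatment scan, the end-of-treatment scan, or the last scan in follow-up.

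Censoring at discontinuation is harmless only if stopping carries no information about later risk. That cannot be assumed here. Section 7.2 lists inability to tolerate cabozantinib as a reason to stop, and 6.1.2.1 says "pembrolizumab will be administered via intravenous infusion Q3W for up to 2 years", so some patients may stop while doing well. These groups need not share one prognosis.

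At stake is the PFS estimate of a single-arm trial, reported as one curve with no control arm in which a similar distortion might partly cancel. If the rule is not settled beforehand, it could be chosen after the curves have been seen.

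**Working it through.** **1. The plan's own figures.** The documents give no PFS median, event count or power. The only sized figure is the ORR design: continue if more than 5 of 14 respond, reject if at least 21 of 44 respond. Exact two-stage binomial calculation gives:

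- at 35%: type I error 0.0458, probability of early stopping 0.641, expected sample size 24.8
- at 55%: power 0.8001

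The design reproduces, and nothing in it uses PFS.

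**2. The rules side by side.**

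| Patient | Sections 3 and 8.1 | 9.4.3, literal |
|---|---|---|
| Progresses or dies on treatment | event | event |
| Stops for another reason, later progresses or dies | event | censored |
| Stops for another reason, never has an event | censored, last tumor assessment | censored, last radiographic assessment (scan not named) |
| On treatment and event-free at cutoff | censored, last tumor assessment | no rule given |

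The second row is the conflict.

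**3. Size, by simulation.** From the documents: scans every 12 weeks. Assumed:

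- Exponential PFS with an on-treatment median of 8 months, so hazard ln 2 / 8 = 0.0866 per month.
- Exponential stopping at 0.03 or 0.05 per month. The share stopping first is 0.03 / (0.03 + 0.0866) = 26%, about 11 of 44, or 0.05 / (0.05 + 0.0866) = 37%, about 16 of 44.
- Hazard after stopping 0.5 to 2 times the on-treatment hazard.
- 85% of events are progressions, dated to the next scan; deaths are dated exactly.

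Each scenario has 400,000 patients. Three readings of 9.4.3 are compared with the 8.1 rule: (a) censor at the last on-treatment scan; (b) censor at an end-of-treatment scan 1 month after stopping; (c) censor at the last scan including follow-up, ignoring later progression or death.

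12-month PFS with 37% stopping:

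| Hazard ratio after stopping | 8.1 rule | (a) | shift | (c) | shift |
|---|---|---|---|---|---|
| 0.5 | 43.0% | 35.5% | -7.5 | 49.1% | +6.1 |
| 1 | 38.0% | 35.6% | -2.4 | 48.2% | +10.2 |
| 2 | 31.7% | 35.7% | +4.0 | 46.6% | +14.9 |

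Over both stopping rates the shifts in points are:

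- (a): -7.5 to -4.7 at ratio 0.5; -2.4 to -1.4 at 1; +1.0 to +1.2 at 1.5; +2.6 to +4.0 at 2
- (b): -5.5 to +5.8
- (c): about +4 to +15, upward in every scenario

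Under (a) the curve hardly responds to what happens after stopping (35.5 to 35.7%), while the 8.1 curve moves from 43.0 to 31.7%. That is why the sign changes.

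**4. Sensitivity.** A separate run used 30% stopping by 12 months, 36 months of follow-up, and counted a patient as having stopped if treatment ended before the event was documented. Its 12-month values at ratios 0.5, 1 and 2 were:

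- 8.1 rule: 41.1, 38.0, 33.9%
- (a): 37.6, 37.8, 37.7% (shifts -3.5, -0.2, +3.8)
- (c): 46.3, 45.7, 44.6% (shifts +5.2, +7.7, +10.7)

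The literal rule kept 72 to 78% of the events. At 24 months the 8.1 rule gave 19.8, 14.4 and 10.3%, against 14.2, 14.3 and 14.4% under (a) and 29.1, 26.5 and 22.8% under (c).

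How stopping between an event and the scan that documents it is coded changes individual shifts by about 2 to 3 points. A progression share of 70 to 100% changes any shift by less than 1 point. For medians of 4 to 16 months the signs of (a) at ratios 0.5 and 2, and of (c), hold. The absolute 12-month level then runs from roughly 11 to 65%. The mITT requirement of a post-baseline scan was not modelled.

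**5. Scale.** A binomial 95% half-width for 33% with 44 patients is 1.96 × √(0.33 × 0.67 / 44) = 0.139, about 14 points.

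**6. DCR wording.** With a hypothetical 20 responders and 10 stable disease among 44, DCR as defined is 30/44 = 68% (exact 95% CI 52 to 81). If the carried-over sentence were applied literally it would be 20/44 = 45% (30 to 61).

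**The case against.** The strongest defence is that 9.4.3 is not a complete censoring scheme. It has no rule for event-free patients still on treatment, so it has to be read with 8.1. The disputed sentence may then only fix a censoring date for patients who stop and never have an event. That reading removes the conflict and may be what was meant. But the sentence does not contain that condition, and it is the one the analysis will be programmed from.

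Several narrower points stand:

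- Reading (c) is an extreme. It censors a patient at the very scan that documents progression, which the preceding sentence defines as the event. The +15 is a worst case. Readings (a) and (b) move 12-month PFS by at most about 7.5 points, inside the 14-point sampling half-width. A shift from the rule is nevertheless systematic and is not reflected in the confidence interval.
- The 8-month median is an assumption. The direction results survive other medians; the PFS levels do not.
- The 2-year limit applies to pembrolizumab, and 6.1.2.1 lets cabozantinib continue at the investigator's discretion. Reaching 2 years is therefore not clearly stopping study treatment. Intolerance is the cleaner example.
- Few analysts would let the carried-over DCR sentence override the definition just before it. That point and the duration label are editorial.

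**Conclusion.** The concern holds. As written, 9.4.3 censors patients whom Sections 3 and 8.1 would count as events, and it discards follow-up that Sections 1.3, 7.2 and 8.3.4.2 plan to collect. No single direction of bias can be stated. With censoring at the last on-treatment scan, PFS is understated if patients do better after stopping and overstated if they do clearly worse: about -7.5 to +4 points at 12 months under the assumptions above. If follow-up scans set the date and later events are ignored, PFS is overstated in every scenario, by about 4 to 15 points. These sizes rest on assumed stopping rates, medians and hazards; the contradiction in wording does not. The endpoint is secondary and descriptive, with no test, so this should be corrected but does not threaten the ORR conclusion. The DCR and duration wording are minor.

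**What to change.** Replace the 9.4.3 censoring sentence with the rule of Sections 3 and 8.1: progression or death counts whenever it occurs, regardless of treatment discontinuation, and only patients with neither are censored, at the last tumor assessment. No PFS rule for new anticancer therapy was found, so the same sentence should say how it is handled. Keep censoring at discontinuation as a sensitivity analysis at most, with the censoring scan named.

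Minor edits: in the DCR paragraph, refer to disease control (CR, PR or SD) in place of objective response. In 8.1, rename the time starting at CR, PR or SD as duration of disease control, and start any duration of response at first CR or PR as in Appendix A.

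The cost is SAP wording, with no new patients or design change. One operational gap should be closed with it. The follow-up column of the Section 1.3 calendar marks only survival status, and 8.3.4.2 allows follow-up by telephone or correspondence. The calendar should cross-refer to the continued scans in 7.2; otherwise off-treatment progression dates may be incomplete.

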8 STUDY ASSESSMENTS AND PROCEDURES

8.1 EFFICACY ASSESSMENTS

The intention of the study design is to closely monitor patients with safety follow-up and disease assessments in the absence of disease progression or other study discontinuation criteria.

For the purposes of this study, patients should be re-evaluated after the first 12 weeks of treatment and then every 12 weeks. **In addition to a baseline scan, confirmatory scans will** also be obtained at least 4 weeks and no more than 14 weeks following initial documentation of partial or complete response.

Primary efficacy endpoint is best ORR defined as the proportion of all treated subjects whose best response at any time during the study following initiation of therapy is confirmed CR or confirmed PR. This will be assessed according to the RECIST v1.1.(Appendix A).

PFS, defined as the time between the first dose of study therapy and the earliest date of progression or death. Subjects who have neither progressed nor died will be censored at the last tumor assessment date for PFS. The endpoint ORR and PFS will be assessed according to the RECIST v 1.1 criteria.

Additional efficacy endpoints will include the disease control rate (DCR) defined as the percentage of patients achieving CR + PR + SD at any time during the study following initiation of therapy. This will be assessed according to RECIST v1.1 criteria. The duration of response (DOR), is defined as the time between the date that the criteria are first met for CR or PR or SD and the earliest date of progression or death.

OS, defined as the time between the first dose of study therapy and death (subjects who have not died will be censored at the most recent last-known-alive date), will also be analyzed.

The tumor assessment (TA) performed during screening will be used as a baseline for efficacy assessments. CT/MRI imaging of the chest and abdomen is required at Screening and at each TA, regardless of the location of known metastases. In addition, CT/MRI scans must be obtained of anatomic regions not covered by the chest and abdomen scans in subjects where there is clinical suspicion of deep soft tissue metastases (eg, lesions in the thigh). Such additional CT/MRIs will be required at Screening when deep soft tissue disease is known/suspected and must be consistently repeated at all TAs if a deep soft tissue lesion is identified during Screening.

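### Section 9.4.3 censors PFS by the reason for stopping treatment, so progressions and deaths that sections 3 and 8.1 count as events are lost

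*Combined protocol and SAP*

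**What the plan says.** Section 9.4.3 measures PFS from treatment initiation to the "date of first documentation of disease progression or death due to any cause in the absence of documented progression". That definition is not confined to time on treatment. The next sentence then says of patients who "discontinue study treatment due to reasons other than progression or death, the patient will be censored at their last radiographic assessment for progression".

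Sections 3 and 8.1 share a different rule: "Subjects who have neither progressed nor died will be censored at the last tumor assessment date for PFS".

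On data collection, section 7.2 states that patients who leave study treatment but keep their consent to follow-up "for reasons other than progression will continue to have scans per study calendar until PD is noted". Footnote 3 of the study calendar (section 1.3) adds "Subjects will be followed for survival and progression post treatment every 3 months x 2 years", and section 8.3.4.2 says much the same: "Patients will be followed for survival and progression every 3 months for 2 years". The calendar row "Tumor Imaging- CT Chest/Abdomen/Pelvis" is also marked at the End of Treatment (EOT) visit. Footnote 2 times that visit: "End of treatment visit will be completed 30 days (+/- 7 days) from date of last dose of study drug" (or earlier, if another treatment starts first).

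**The concern.** Sections 3 and 8.1 decide censoring by whether the patient has had an event. Section 9.4.3 decides it by why treatment stopped, with no condition that the patient is event-free. Stops without progression are foreseen: section 7.1 lists unacceptable toxicity and section 7.2 lists intolerance of cabozantinib.

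Two things are at stake. First, an analyst following 9.4.3 and one following 8.1 would report different event counts and different Kaplan-Meier curves. Second, stopping for toxicity may be related to the later risk of progression. Censoring at that point can then be informative, which Kaplan-Meier assumes it is not.

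**Working it through.** **The plan's own figures.** No figure is stated for PFS. The only design figure is for ORR: stop at 5 or fewer responses in 14, reject at 21 or more of 44. Exact two-stage binomial sums give type I error 0.0458 at 35% and power 0.8001 at 55%, so the stated 0.05 and 80% reproduce. Nothing below affects them.

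**One patient under each rule.** A patient stops both drugs for toxicity at week 22. Scans fall every 12 weeks. The EOT scan is at about week 22 + 30/7 = 26. The week-48 scan shows progression.

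| Rule | Result |
|---|---|
| 3 and 8.1 | event at week 48 |
| 9.4.3, last scan before stopping | censored at week 12 |
| 9.4.3, EOT scan | censored at about week 26 |
| 9.4.3, last scan of all | censored at week 48 |

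No reading of 9.4.3 as written counts the event. The trigger misfires elsewhere too. Section 7.2 allows treatment beyond radiographic progression, so a patient with progression on record who later stops for toxicity also meets the 9.4.3 condition.

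**Size: inputs.** The 12-week scans and the EOT scan 30 days after last dose come from the calendar, and 44 from section 9.2. The rest is assumed:
- median PFS m of 6, 12 or 18 months, exponential;
- share q stopping for other reasons before an event of 10%, 20% or 30%;
- hazard after stopping 1, 1.5 or 2 times that on treatment;
- 15% of events are deaths;
- follow-up uniform from 24 to 42 months.

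The event rate is λ = ln 2 / m and the stopping rate is λq/(1 − q). For m = 12 and q = 0.20 these are 0.0578 and 0.0578 × 0.25 = 0.0144 per month. Progression is dated at the scan that shows it. The analysis keeps patients with at least one post-baseline scan (mITT, 96% to 98.5% of patients).

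**Middle case (12 months, 20%, 1.5 times), per 44 patients.** Events are 37.46 under 8.1 and 31.14 under 9.4.3. The loss is 37.46 − 31.14 = 6.32, and 6.32 / 37.46 = 17%.

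| Rule | 12-month PFS | 24-month PFS |
|---|---|---|
| 8.1 | 52.3% | 25.8% |
| 9.4.3, last scan before stopping | 52.8% | 27.3% |
| 9.4.3, EOT scan | 53.4% | 27.9% |
| 9.4.3, last scan of all | 56.0% | 33.1% |

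**Range over the 27 combinations.** Events lost run from 1.6 to 13.3 of 44 patients (5% to 31% of events). The 12-month shift against 8.1 is:
- −2.1 to +3.6 points with the last scan before stopping;
- −0.3 to +5.3 points with the EOT scan;
- +0.7 to +13.7 points with the last scan of all.

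**Why the sign varies.** If the hazard rises after stopping, removing these patients flatters the curve. If it does not, censoring back at an earlier scan drops patients who were event-free for part of the interval, which lowers the curve slightly.

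**Yardstick.** The binomial standard error at 12 months is √(0.5225 × 0.4775 / 44) = 0.075, or 7.5 points.

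**Simpler cross-check.** With events seen exactly, medians of 6 or 10 months, 10% to 30% stopping by 12 months and 24 months of follow-up, about 2 to 10 of 36 to 42 events are lost. The median is unchanged at an equal hazard and overstated by up to about 0.9 months at a doubled one.

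**The case against.** The strongest reply is that 9.4.3 is unclear rather than wrong. The sentence just before it makes any first progression or death the event. The censoring sentence could simply supply a date for patients who stop and never have an event. Section 9.4.3 says nothing about event-free patients still on treatment, so it has to be read with 8.1 anyway. That may well be what the authors meant, but the sentence does not say it, and the same edit is needed on either reading.

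Several points about size do stand:
- The last-scan-of-all reading is the least plausible, because it would censor a patient on the very scan that shows progression. It alone produces the double-digit shifts.
- The simulated counts make no allowance for withdrawal of consent, after which section 7.2 collects only survival status from public records. If 30% of those who stop withdraw consent, and only the 15% of their events that are deaths stay visible, the middle-case loss falls to about 6.32 × (0.70 + 0.30 × 0.15) = 4.7 events.
- The upper figure of 13.3 needs almost every one of the assumed 30% who stop (0.30 × 44 = 13.2) to have an observed later event.
- The calendar's follow-up column marks only survival status, and 8.3.4.2 describes telephone contact, correspondence and death records. The firm support for scans after treatment is section 7.2.
- No test or decision rests on PFS.

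Sections 3, 8.1 and 9.4.3 are also silent on progression after a new anticancer therapy. That is a separate gap, which the fix below does not close.

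**Conclusion.** The concern holds at minor severity. As written, 9.4.3 contradicts sections 3 and 8.1, discards events that section 7.2 arranges to collect, and does not name the scan that sets the censoring date.

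The contradiction is in the text and needs no assumption. Its numerical effect rests wholly on assumed PFS, stopping and hazard figures. On the two more plausible readings, the 12-month shift stays below one standard error and its sign is not fixed. The loss of events is the clearer consequence. Only the descriptive PFS curve is affected.

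**What to change.** Replace the censoring sentence in 9.4.3 with:

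> Progression or death after stopping study treatment counts as a PFS event. Only patients who have neither progressed nor died are censored, at their last tumor assessment, including scans after treatment under section 7.2.

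The present rule can be kept as a labelled sensitivity analysis, provided that it names the scan used for censoring.

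The cost is one sentence. No visits or patients are added, because section 7.2 already requires the scans for patients who keep consent to follow-up. Patients who withdraw consent, with no known progression or death, stay censored at their last tumor assessment. If the authors only ever meant event-free patients, the edit simply makes that explicit.
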